#### **6.5 Cycle 2, Day 1 (C2D1) and all subsequent Day 1 cycle visits (i.e., C3D1, C4D1)**

The subject will have the C2D1 Safety Procedures detailed below performed prior to initiating study treatment. Required assessments and study drug (Avelumab) administration windows include  $\pm 3$  days of scheduled visit.

- Adverse event assessment
- Complete physical exam, including neurological exam, and KPS assessment

CONFIDENTIAL

- Vital signs: When scheduled at the same visit as other procedures, vital signs should be measured prior to clinical laboratory assessments or research blood sample collection.
  - Weight (can be taken within 3 days of scheduled Avelumab administration)
  - Vital signs on treatment days subsequent to C1D1 will be assessed and documented prior to the infusion and then approximately 30 minutes after the completion of the infusion (all infusion VS timepoints  $\pm 10$  minutes):
    - Temperature, resting blood pressure, pulse and respiration rate.
    - Note: following all Avelumab infusions, subjects must be observed for 30 minutes post-infusion for potential infusion-related reactions.
- Serum chemistry: sodium, potassium, chloride, bicarbonate, calcium, magnesium, phosphorous, glucose, albumin, creatinine, blood urea nitrogen (BUN), uric acid, ALT, AST, total bilirubin, direct and/or indirect bilirubin, alkaline phosphatase (ALP), and lactate dehydrogenase (LDH)
- Hematology: WBC count, 3-cell differential (ANC, monocyte count, lymphocyte count), hemoglobin, hematocrit, and platelet count
- Urinalysis: glucose, blood, pH, specific gravity, ketones, and urine protein
- Pregnancy test (urine or serum  $\beta$ -HCG) for women of child-bearing potential
- Research Blood Samples (C2D1 only, not required at subsequent visits): Note: Research blood samples will be taken at only 2 timepoints: **C1D1 (pre-dose)** and **C2D1**. All subjects will have the below research blood samples collected. For details on specimen collection, processing, handling and shipping, refer to **Section 6.8, Attachment 7** and the study **Lab Manual**.
  - NYULMC subjects: 40 mL (four 10 mL purple top EDTA tubes) of whole blood will be drawn and immediately sent to the below sites:
    - One (1) 10 mL tube will be sent to the CBRD at NYULMC for acquisition of whole blood, buffy coat, and plasma samples.
    - Three (3) 10 mL tubes will be sent to the IMC at NYULMC and immediately processed for isolation of PBMCs.
  - Subjects at other sites: 40 mL of whole blood will be collected in two types of tubes provided by NYULMC. All tubes will be shipped overnight to the CBRD at NYULMC per instructions in the **Lab Manual**.
    - 10 mL will be drawn into one Streck Cell-Free DNA BCT® collection tube
    - 30 mL total will be drawn into three 10 mL purple top EDTA tubes and immediately sent to NYULMC.

Avelumab will be administered in an outpatient setting as an IV infusion (see **Treatment Regimen, Section 5.2**). Each patient's dose will depend on individual body weight. The dose of Avelumab must be adjusted each cycle for changes in body weight of  $\geq 10\%$ . Dose adjustments for changes in body weight of  $< 10\%$  will be at the discretion of the investigator.

### **6.6 Cycle 3, Day 1 (C3D1) and then every 8 weeks thereafter**

At C3D1, all required procedures listed in the visit for **Cycle 2, Day 1+** (Section 6.5) will be required except research blood samples. In addition:

CONFIDENTIAL

This material is the property of the NYU School of Medicine and Langone Medical Center. Do not disclose or use except as authorized in writing by the study sponsor

- **Efficacy assessment** consisting of a contrast-enhanced brain MRI or CT will be performed prior to C3D1. Efficacy assessments will then be performed every 8 weeks thereafter. MRIs or CTs can be performed within 7 days (-7 days) of scheduled visit. On-study imaging should follow calendar days (every 8 weeks) and should not be adjusted for delays in cycle starts.
  - Local reading (investigator assessment) will be used to determine eligibility and for participant management. Response Assessments will be performed on every brain imaging assessment performed on protocol per iRANO criteria (see **Section 6.7, Efficacy Procedures**, and **iRANO criteria in Attachment 3**).
- Thyroid stimulating hormone (TSH), free T4

## 6.7 End of Treatment Procedures

Avelumab administration will continue for 2 years or until progression of disease, unacceptable adverse event(s), subject withdrawal of consent, or other event that meets criteria for subject withdrawal or treatment discontinuation as per guidelines outlined in **Section 4.5** and **Section 5.2.3**.

End of treatment assessments below will be performed within 7 days after last drug administration or within 7 days after decision to end treatment.

- Adverse event assessment
- Complete physical exam, including neurological exam, and KPS assessment
- Vital signs: weight, temperature, resting blood pressure, pulse and respiration rate.
- Serum chemistry: sodium, potassium, chloride, bicarbonate, calcium, magnesium, phosphorous, glucose, albumin, creatinine, blood urea nitrogen (BUN), uric acid, ALT, AST, total bilirubin, direct and/or indirect bilirubin, alkaline phosphatase (ALP), and lactate dehydrogenase (LDH)
- Hematology: WBC count, 3-cell differential (ANC, monocyte count, lymphocyte count), hemoglobin, hematocrit, and platelet count
- Urinalysis: glucose, blood, pH, specific gravity, ketones, and urine protein
- Thyroid stimulating hormone (TSH), free T4
- Pregnancy test (urine or serum  $\beta$ -HCG) for women of child-bearing potential

## 6.8 Post Treatment Procedures

**Follow up post-treatment:** All participants will be followed until resolution or stabilization of any serious or reportable adverse events occurring during treatment or starting within 30 days of last study drug. After the end of treatment, each subject will be followed for 30 days for adverse event monitoring and 90 days for serious adverse event reporting. Assessments may continue for ongoing reportable adverse events. Participants removed from protocol therapy for unacceptable adverse events will be following until resolution or stabilization of the adverse event.

**30-day post-drug visit:** A site visit is to be performed at 30 days ( $\pm 7$  days) after the last study drug is given, unless the subject is unable to travel due to deteriorating medical condition, due to the potential risk for delayed immune-related toxicities. The visit will include the safety procedures detailed below:

- Adverse event assessment.
- Symptom-directed physical exam and KPS assessment.
- Vital signs: weight, temperature, resting blood pressure, pulse and respiration rate.

CONFIDENTIAL

- Serum chemistry: sodium, potassium, chloride, bicarbonate, calcium, magnesium, phosphorous, glucose, albumin, creatinine, blood urea nitrogen (BUN), uric acid, ALT, AST, total bilirubin, direct and/or indirect bilirubin, alkaline phosphatase (ALP), and lactate dehydrogenase (LDH).
- Hematology: WBC count, 3-cell differential (ANC, monocyte count, lymphocyte count), hemoglobin, hematocrit, and platelet count.

**90-day post-drug safety follow-up:** An extended safety follow-up is to be performed at 90 days ( $\pm 14$  days) after the last study drug is given. This may be performed via documented phone conversation with a study nurse or clinician or physician.

**Extended follow-up post-treatment:** Subjects should be contacted every 3 months ( $\pm 14$  days) for survival status and initiation of any new anti-cancer treatments until death, withdrawal of permission to record at least survival data, or subject is lost to follow-up. Contact may include clinic visit, telephone contact, e-mail, mail or medical record review. The date of death, initiation of any new anti-cancer treatments and date of last contact should be documented.

If a subject withdraws permission to record at least survival data after coming off treatment, this must be documented along with the date the subject withdraws permission. Subjects will be considered lost to follow up if no medical records are available to be reviewed and two phone calls each to the subject and then the subject's next-of-kin (if the subject does not respond) are not returned over two consecutive 3 month periods.

## 6.9 Efficacy Procedures

Tumor response will be assessed every 8 weeks (see **Section 6.6**) using **iRANO criteria** as outlined. Clinicians may repeat response assessment more frequently as clinically indicated.

Refer to **Attachment 3** for details on iRANO criteria, guidelines for assessing radiologic findings, and treatment algorithm for the assessment of progressive imaging findings in patients with neuro-oncological malignancies undergoing immunotherapy.

**Evaluable for objective response.** Only those participants who have measurable disease present at baseline (obtained within 14 days of cycle 1, day 1) scan and have received at least one dose of therapy will be considered evaluable for response. These participants will have their response classified according to the definitions stated in **Attachment 3**. (Note: Participants who exhibit objective disease progression or die prior to the end of cycle 1 will also be considered evaluable.)

**Note on continuation of therapy pending confirmation of radiographic disease progression: iRANO** recommends confirmation of disease progression on **follow-up imaging 3 months after initial radiographic progression** if there is no new or substantially worsened neurological deficits that are not due to comorbid events or concurrent medication, and it is 6 months or less from starting immunotherapy (see **Attachment 3** for **iRANO** criteria details). A decision of whether a patient should continue immunotherapy pending confirmation of radiographic disease progression should be established based on perceived benefits and risks. Continuation of immunotherapy may be considered pending follow-up imaging as long as subjects are deriving apparent clinical benefit with minimal and acceptable toxic effects.

By contrast, investigators may consider interrupting immunotherapy for subjects who need a substantial increase in corticosteroids (i.e.,  $>4$  mg of dexamethasone or equivalent per day) for evolving symptoms associated with brain edema or who have more than mild treatment-related toxic effects such as at least grade 2 irAEs. These guidelines are included to limit the likelihood of progressive immunotherapy-induced inflammatory changes leading to substantial deficits in otherwise stable or symptom-free patients. In such subjects, an interruption of immunotherapy dosing might be considered pending follow-up imaging.

CONFIDENTIAL

This material is the property of the NYU School of Medicine and Langone Medical Center. Do not disclose or use except as authorized in writing by the study sponsor

Furthermore, investigators may discontinue or interrupt immunotherapy at any time if this option seems to be in the best medical interest of the subjects. As a general guidance, resumption of immunotherapy might be taken into account when systemic dexamethasone is decreased to 4 mg/day or less and the contrast-enhancing tumor burden is classified as stable disease, partial response, or complete response on a follow-up scan, or when relevant treatment-related toxic effects have resolved to grade 1 or less or pre-treatment baseline.

## 6.10 Research Specimen Procedures

See **Attachment 7** for Background and Rationale of Research Correlative Studies. Refer to the study procedures above in **Section 6.1** and **Section 6.5** for research blood sample collection. Also, refer to the study **Lab Manual** for specific processing and handling procedures for research blood specimens.

Note: This study involves collection of required archival tumor tissue and blood specimens for research as well as collection of an *optional* tumor specimen if a biopsy is required during or after protocol therapy. All patients will be given the option to have leftover research specimens after study completion and completion of protocol-defined research studies banked for future research at the time of informed consent. See **Section 9.1.1** for details on leftover research samples.

### 6.10.1 Archival Tumor Specimen

Archival tumor tissue from a previous surgical resection that demonstrates histopathological evidence of transformation to glioblastoma (GBM, WHO grade IV) or genetic alteration as specified in the **Eligibility Criteria (Section 4.1)** must be submitted.

A paraffin-embedded or frozen tumor-tissue block with a minimum of 1 cm^2 surface area of viable tumor is required. The tumor block should contain at least 20% viable tumor, i.e., a representative H&E slide should show that at least 20% of the specimen contains viable tumor.

If a tumor block cannot be submitted, then twenty (20) unstained 5-micron slides (preferably 10 slides from two different tumor blocks from the same surgery) from the tumor specimen must be submitted.

Note, an archival tumor specimen from the prior lower-grade glioma tumor is not required.

Send archival tumor specimens for research to:

[name]  
Department of Pathology, NYU Langone Medical Center  
[name]  
[name]  
[name]  
[contact]  
[contact]  
[contact]  
[contact]

### 6.10.2 Research Blood Samples

Research blood samples will be taken at only 2 timepoints: **C1D1** (up to 3 days prior to C1D1) and at the **C2D1 visit**.

Refer to the **Lab Manual** for specific processing and handling procedures for research blood specimens. All subjects will have the below research blood samples collected. For details on specimen collection, processing, handling and shipping, refer to **Section 6.8** (Study Procedures), **Attachment 7** (Background and Rationale) and the study **Lab Manual**.

CONFIDENTIAL

This material is the property of the NYU School of Medicine and Langone Medical Center. Do not disclose or use except as authorized in writing by the study sponsor

Whole blood for research will be collected from all subjects as described below:

- NYULMC subjects: 40 mL (four 10 mL purple top EDTA tubes) of whole blood will be drawn and immediately sent to the below sites:
  - One (1) 10 mL tube will be sent to the CBRD at NYULMC for acquisition of whole blood, buffy coat, and plasma samples.
  - Three (3) 10 mL tubes will be sent to the IMC at NYULMC and immediately processed for isolation of PBMCs.
- Subjects at other sites: 40 mL of whole blood will be collected in two types of tubes provided by NYULMC. All tubes will be shipped overnight to the CBRD at NYULMC per instructions in the **Lab Manual**. **\*Subsites should NOT schedule research blood draws on Fridays as the NYU CBRD will not be able to receive specimens on weekends.**
- 10 mL will be drawn into one Streck Cell-Free DNA BCT® collection tube
- Three (3) 10 mL purple top EDTA tubes of whole blood will be drawn and immediately shipped to NYULMC and then immediately processed for isolation of PBMCs.

### 6.10.3 Optional Tumor Biopsy for Research

If subjects undergo tumor resections or biopsies during the study period after treatment initiation, or after progression on HFRT + Avelumab, a tumor specimen will be collected for research purposes. For details see **Attachment 7**. A section of frozen tumor or a FFPE block (surface area of 1 cm^2 containing at least 20% viable tumor, as described above in Section 6.8.2) from the tumor surgery is preferred. If a frozen tumor specimen or a tumor block cannot be provided, then 20 unstained 5-micron slides (preferably 10 slides from two different tumor blocks from the same surgery) from the tumor block should be sent.

Send optional tumor samples to:

[name]  
Department of Pathology, NYU Langone Medical Center  
[name]  
[name]  
[name]  
[contact]  
[contact]  
[contact]  
[contact]

## 7 Statistical Plan

### 7.1 Sample Size Determination

#### 7.1.1 Background for Statistical Plan:

Secondary GBM outcomes: Although patients with *IDH* mutant gliomas survive relatively longer than those with *IDH* wildtype gliomas from the time of initial diagnosis, nearly all *IDH* mutant gliomas eventually become lethal, with most transforming to "secondary GBM". Outcomes for patients with secondary GBM (transformed *IDH* mutant gliomas), including PFS and OS, have been shown to be equivalent to patients with recurrent "*de novo* GBM", the vast majority of which are *IDH* wildtype. The median OS from the time of recurrence or transformation is equivalently

CONFIDENTIAL

This material is the property of the NYU School of Medicine and Langone Medical Center. Do not disclose or use except as authorized in writing by the study sponsor

dismal, ranging from 7-9 months. Therefore, efficacy endpoints for *IDH* wildtype GBM therapeutic clinical trials can be considered equivalent for the *IDH* mutant secondary GBM population.

**PFS6 reference measures:** Previous meta-analyses have demonstrated that PFS6 is an adequate indicator of antitumor benefit for salvage GBM clinical trials and is the standard benchmark used in GBM chemotherapy trials. Published reference outcomes in recurrent GBM report a PFS6 of 9-15%. Temozolomide, the only chemotherapy that has demonstrated improved survival in any prospective, randomized phase III trial in GBM, produced a PFS6 of 21% when tested in recurrent GBM patients. More recently, a number of recently reported randomized, prospective trials in recurrent GBM used conventional cytotoxic chemotherapies such as lomustine and carboplatin for the control arm and have reported remarkably similar estimated PFS6 rates in the chemotherapy control arms, ranging between 15%-25%. Otherwise, bevacizumab, which was granted accelerated approval by the US FDA for use as monotherapy in progressive GBM in 2009 based on two historically-controlled, single-arm or non-comparative phase II trials, has been reported to have relatively higher estimated PFS6 rates of 29% and 42.6%. However, despite improved PFS6 rates observed in phase II trials, the addition of bevacizumab to lomustine failed to show a benefit in overall or neurologic progression-free survival compared to lomustine alone in a multi-institutional, randomized phase III trial of recurrent GBM. Therefore, based on the aggregate results of the above studies, the reference benchmark for our study will be PFS6 of 40%.

**Overall Survival (OS) reference measures:** In recent randomized, controlled trials of recurrent GBM, all of which have failed to demonstrate differences between arms, the median OS of experimental and control arms from the time of recurrence across all of these studies have been remarkably similar and have ranged between 6-10 months, with most arms in these studies reporting a median OS of approximately 9 months. These data indicate the chemotherapies in these studies have similar minimal efficacy in recurrent GBM.

With regards to salvage radiotherapy in recurrent GBM, a wide range of outcomes have been reported from numerous retrospective and phase II trials, likely due to small sample sizes, significant selection bias and differences in dose prescriptions and schedules. Notably, however, reported OS rates from the time of salvage re-irradiation are highly similar to recent randomized trials using salvage chemotherapy, with one analysis of >300 recurrent GBM patients reporting PFS6 rates between 28% to 39% and a median 1-year overall survival rate of 26%. Median OS rates reported in re-irradiation studies with larger numbers of patients are also similar to salvage chemotherapy studies, ranging between 7-11 months. Based on these and other studies, the RTOG 1205 randomized trial of re-irradiation with bevacizumab versus bevacizumab alone uses 9 month OS as the ineffective measure. Based on the aggregate data above, we chose as a reference measure a 1-year median OS rate of 25%.

### 7.1.2 Safety Lead-In sample size determination

Based on the design of the Safety Lead-In and Dose De-Escalation Rules (Refer to Section 5.2.1 and Section 5.2.1.1), the minimum number of patients in the Safety Lead-In will be 6 subjects if the initial dose level (Dose Level 0) is found to be safe and considered the RP2D (**Section 7.1.3**).

If the Safety Lead-In enters into the Dose De-Escalation phase (**Section 5.2.1.1**), then the minimum number of total subjects in the entire study will be 12 if a RP2D cannot be determined. The maximum number of subjects in the Safety Lead-In based on the dose de-escalation design will be 18, with 6 subjects at each Dose Level (**Section 5.2.1.1, Table 1**). If a RP2D is determined after 18 subjects, a total maximal sample size in the entire study of 61 subjects including both the Safety Lead-In and Phase II portions of the study.

## 7.2 Statistical Methods

### 7.2.1 Safety Lead-In

The Safety Lead-In portion of the study is based on a 3 + 3 design with 3 to 6 patients assigned per dose level. The exact number of patients enrolled in the study will depend on the number of protocol-defined DLTs observed and the need to expand currently defined dose levels, or open additional cohorts at lower dose levels as described in **Section 5.2.1 (Safety Lead-In Design)** and **Section 7.1.2 (Sample Size Determination)**.

The subjects treated at the RP2D in the Safety Lead-In will be included as a separate cohort for the evaluation of outcomes in the phase II study. Data for the Safety Lead-In will be summarized using descriptive statistics. In general, data will be summarized by dose levels. See below in **Section 7.3.1** for Safety Lead-In population for Analysis.

### 7.2.2 Phase II trial

See **Section 7.1.3** for sample size determination. Six months will be defined as six 28-day cycles. Patients will be evaluated for radiographic responses by conventional contrast enhanced MRI every 8 weeks. Radiographic response assessments will be determined using recently developed iRANO criteria for GBM. All subjects who initiate therapy (receive at least one dose of Avelumab and/or radiotherapy) will be evaluated for radiographic response and safety. PFS6 and radiographic response rates will be estimated with exact 95% confidence intervals.

PFS, defined as the time between treatment initiation and first occurrence of disease progression or death, will be censored at last follow-up if the patient remained alive without disease progression. OS will be determined from the time of treatment initiation until the time of death, with OS being censored at last follow-up if the patient remained alive. The Kaplan–Meier curves will be used to summarize PFS and OS and to estimate the medians and 6-month OS and PFS (PFS6).

For toxicity monitoring statistical methods, see the **Primary Safety Endpoints** in **Section 3.4**.

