### **4.5.2 Data Collection and Follow-up for Withdrawn Subjects**

For End of Treatment required assessments see **Section 6 (Study Procedures)**, and **Schedule of Events (Attachment 1)**. After the end of treatment, each subject will be followed for 30 days for adverse event monitoring and 90 days for serious adverse event reporting. Assessments may continue for ongoing reportable adverse events. A visit is to be performed at 30 days ( $\pm 7$  days) after the last study drug is given. Participants removed from protocol therapy for unacceptable adverse events will be following until resolution or stabilization of the adverse event.

Subjects who discontinue for reasons other than progressive disease will have post-treatment follow-up for survival. After coming off study, each subject will be contacted every 3 months by telephone or medical record review to assess survival status until they meet criteria for removal from study as detailed below.

- Withdrawal of permission to record at least survival data
- Lost to follow-up
- Death

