#### 5.2.3.7 Permanent Discontinuation of Study Treatment

In the event of an infusion reaction of Grade  $\geq 3$  severity during or directly following Avelumab infusion, dosing should be stopped and the patient must permanently discontinue Avelumab treatment.

Study treatment will be permanently stopped in the event of evidence of pregnancy.

In addition, study treatment for any subject may be discontinued for other safety reasons or compliance issues at the discretion of the investigator, overall PI or sponsor. A subject may choose to discontinue study treatment or study participation at any time for any reason.

A subject who permanently discontinues Avelumab treatment may continue follow-up in the study without additional treatment until progression of disease or closure of the study (**Section 4.5**). A patient who permanently discontinues study treatment and who does not withdraw from study participation will be asked to return to the clinic for all remaining study visits per the visit schedule (**Attachment 1**) or continue in the follow-up phase of the study until progression of disease or closure of the study (**Section 4.5.2**).

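### PFS is censored at last follow-up, which after early stopping may be a contact without a scan; this biases the Kaplan-Meier PFS6 upward and can lengthen median PFS, but leaves the Simon decision untouched

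*Combined protocol and SAP*

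**What the plan says.** **The analysis rule (Section 7.2.2).** The endpoint is "PFS, defined as the time between treatment initiation and first occurrence of disease progression or death". A patient without an event "will be censored at last follow-up if the patient remained alive without disease progression". The next sentence gives OS the same censoring date. Last follow-up is not defined, nothing ties it to a tumour assessment, and new anti-cancer therapy has no role. The resulting Kaplan-Meier curves are used "to estimate the medians and 6-month OS and PFS (PFS6"), so the label PFS6 is attached to this estimate as well.

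**Follow-up after stopping.** Section 4.5.2: "Subjects who discontinue for reasons other than progressive disease will have post-treatment follow-up for survival". Section 6.8 has subjects contacted every three months "for survival status and initiation of any new anti-cancer treatments until death". It adds: "Contact may include clinic visit, telephone contact, e-mail, mail or medical record review". Attachment 1 marks brain MRI at screening and at Day 1 of Cycle 3 onward. It marks none at end of treatment, 30 days or 90 days.

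**The contrary text (Section 5.2.3.7).** A patient who permanently stops avelumab "may continue follow-up in the study without additional treatment until progression of disease or closure of the study". One who stays in the study "will be asked to return to the clinic for all remaining study visits per the visit schedule", or else continues in the follow-up phase. For that phase the section points to Section 4.5.2, which schedules no scan.

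**The primary analysis (Section 7.1.3).** Patients who do not stay on treatment through six cycles are failures.

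**The concern.** Progression can be ruled out only up to the last time someone looked for it. A survival contact shows that the patient is alive; it does not show that the tumour is stable. If the date of that contact serves as the PFS censoring date, the patient stays in the risk set, event-free, over months when no event could have been recorded short of death.

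Take a patient who stops for toxicity at week 10 after a clean week-8 scan, starts another drug at week 12 and is reached alive at month 9. Read literally, Section 7.2.2 gives this patient nine months of progression-free time. About two were observed, and most of the rest belongs to another treatment.

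This touches the Kaplan-Meier PFS6 and median PFS, a declared secondary endpoint (Section 3.3). The error grows with the number of early stoppers, so in these two estimates poor tolerability can look like benefit.

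**Working it through.** **1. The plan's own design.** Section 7.1.3 stops after stage 1 with 7 or fewer successes in 18 and declares interest with 23 or more in 43. The chance of success at rate p is the sum over x = 8 to 18 of P(X = x; 18, p) × P(Y ≥ 23 − x; 25, p).

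- p = 0.40: 0.0474 (stated 0.047)
- p = 0.60: 0.827 (stated 82.7%)

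The design reproduces. It counts successes under the failure rule and does not use the censoring rule.

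**2. Inputs for the Kaplan-Meier check.** From the documents: scans every 8 weeks (56 days), landmark six 28-day cycles (168 days), and PFS6 of 0.40 and 0.60 as the two reference values. Assumed, because the documents give no figures: exponential PFS; stopping independent of progression, with cumulative risk q = 10, 20 or 30% by day 168; median post-progression survival of 4 or 6 months; 0 or 50% of off-treatment progressions found by record review; 24 months of follow-up. Deaths count as events. Each scenario has 200,000 simulated patients.

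On these inputs 8 to 26% of patients stop early without documented progression: 0.076 × 43 ≈ 3 to 0.259 × 43 ≈ 11.

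**3. Results over all scenarios.**

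| Quantity | True PFS6 0.40 | True PFS6 0.60 |
|---|---|---|
| Kaplan-Meier PFS6, last contact | 0.414–0.486 | 0.609–0.661 |
| Kaplan-Meier PFS6, last scan | 0.396–0.401 | 0.597–0.600 |
| Binary PFS6, early stoppers as failures | 0.28–0.36 | 0.42–0.54 |
| Median PFS, last contact (cycles) | 6.0 | 10.0–12.0 |
| Median PFS, last scan (cycles) | 6.0 | 8.9–9.8 |

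**4. Hand check of the largest case (true 0.40, q = 30%, 6-month post-progression survival, no progressions found).** The binary rate should be 0.40 × (1 − 0.30) = 0.28, as simulated. Early stoppers are 0.231 of patients. If none of them ever had an event, the estimate would be 0.28 + 0.231 = 0.511. The simulated value is 0.486; the difference of 0.025 is stoppers who died before day 168. The bias is 0.486 − 0.40 ≈ 9 points. In the mildest case it is 0.414 − 0.40 ≈ 1 point.

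**5. Why the median moves in one case only.** Progressions are dated on the scan grid. At a true PFS6 of 0.40 the curve is near 0.40^(112/168) = 0.54 after the second scan and 0.40 after the third. Even 0.486 is below one half, so the median stays at the third scan, 6.0 cycles. At 0.60 the curve is near 0.60^(224/168) = 0.51 after the fourth scan, so a small upward shift moves the median. The largest shift is 12.0 − 9.6 = 2.4 cycles.

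**6. Two figures with one name.** In the step 4 case the same data give 0.28 under the failure rule and 0.49 by Kaplan-Meier. Both are called PFS6, and they lie on opposite sides of the 0.40 benchmark.

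**The case against.** **The primary result is safe.** This stands. A reader might infer that the go/no-go decision is inflated. It is not: under Section 7.1.3 the week-10 stopper above is a failure, and early stopping lowers the primary PFS6.

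**Scanning may continue.** A reader might infer that no scans follow discontinuation. Section 5.2.3.7 does not support that, since it offers the remaining scheduled visits. But it offers them as an alternative to a follow-up phase without scans, so the exposure is reduced, not removed.

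**Progression can be found without a scheduled scan.** Attachment 3 counts clinical deterioration, and failure to return because of death or deterioration, as progression. It also has an unknown status for unassessed lesions, and Section 6.8 allows record review. These would catch some events, which is why half detection was modelled. None of them sets a censoring date, and Section 7.2.2 does not say how unknown status is handled.

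**The size could be overstated.** A reader might treat every early stopper as event-free and apply 40% to the others: (16 + 4)/43 = 0.465, (15 + 6)/43 = 0.488 or (14 + 8)/43 = 0.512 for 4, 6 or 8 stoppers. That is too high. Deaths are events under Section 7.2.2, and patients who stop without progression are already a favourable group, so the others are below 40%.

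**Last-scan censoring is not perfect.** If stoppers are nearer to progression than others, it is informative too. In that case last-contact censoring would also be further out than the range shown.

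**Conclusion.** The rule is wrong as written for PFS, although its effect is confined to supportive and secondary estimates. Under the assumptions listed, the Kaplan-Meier PFS6 is about 1 to 9 points too high, and censoring at the last scan removes almost all of this. It does not follow that median PFS is always inflated: it is unchanged at a true PFS6 of 0.40, and about 10 to 12 cycles against 9 to 10 at 0.60.

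The direction is firm wherever progressions after stopping go undetected. The size depends mainly on how many patients stop early without progression and how many later progressions are found, and the documents give neither. How new therapy is handled is a matter of convention; the defect is that the plan states no rule although the start date is collected.

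**What to change.** 1. In Section 7.2.2, censor PFS at the last evaluable iRANO assessment in patients alive without documented progression, and keep last contact for OS only.
2. Where new anti-tumour therapy starts before progression, censor at the last evaluable assessment before it, with a sensitivity analysis that counts its start as an event. State how bevacizumab given for brain edema is classified for this purpose.
3. State that the binary PFS6 of Section 7.1.3 is primary, and label the Kaplan-Meier 6-month PFS as supportive.
4. Reconcile Sections 4.5.2 and 6.8 and Attachment 1 with Section 5.2.3.7 on tumour assessment after discontinuation without progression.

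**Cost.** Items 1 to 3 need analysis-plan text and one sensitivity analysis; new-therapy dates are already collected. Item 4 may add work at the sites if results of routine-care scans are to be gathered. The Kaplan-Meier PFS6 and median PFS may come out less favourable and less precise.
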